Subjects will remain in the study until the clinical confirmatory endpoint of all-cause graft failure is evaluated up to a maximum of 4 years. Graft failure is evaluated by the nephrology EAC. Graft failure, for the purpose of this study, will be defined as 1 or more of the following: (1) institution of permanent dialysis (defined as dialysis treatment >30 days), (2) current transplant nephrectomy, or (3) clinical determination of cessation of kidney graft function and $eGFR \leq 15 \text{ mL/min/1.73m}^2$. If a subject is discontinued for any reason prior to the Month 6 follow-up Visit, every effort will be made to obtain AEs, serum blood urea nitrogen (BUN) and creatinine (Cr) results, $eGFR_{MDRD}$, and a biopsy to send slides and images to the pathology and nephrology EACs for determination of TG and graft function status, respectively (see [Table 2](#) for Early Discontinuation Visit procedures). If a subject is discontinued for any reason prior to the end of the study at 4 years, every effort will be made to obtain AEs, serum BUN and Cr and $eGFR_{MDRD}$ results to send to the nephrology EAC for determination of graft function status (see [Table 2](#) for End of Study Visit procedures).

There will be 3 analyses (2 interim, 1 final) of proportions of subjects with all-cause graft failure, at approximately 50% (~26 events), 75% (~39 events) and 100% (~51 events) of the study data. Following the Month 6 evaluation, subjects will enter a long-term follow-up stage of the protocol, which will include allograft function evaluations every 6 months up to a maximum of 4 years. The duration of the study will be event driven, and is based upon an assumption that there will be approximately 51 all-cause graft failures. The study will continue until 51 such events are accrued and adjudicated by the nephrology EAC. However the maximum amount of time each subject will be followed in the study will be 4 years post initial treatment with investigational product. See Section [9.5.2](#) for additional details.

Resolution will be achieved when, after treatment, the local $eGFR_{MDRD}$ value increases to at least within 20% or above the $eGFR_{MDRD}$ value collected as a pre-AMR baseline. If an AMR episode is diagnosed, in absence of significant decline ($\geq 20\%$) of $eGFR$ from pre-AMR baseline, a follow-up biopsy within 3 months is recommended in order to assess resolution.

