9.8.2 Secondary Efficacy Endpoints

9.8.2.1 Key Secondary Efficacy Endpoint

The key secondary endpoint is defined as the proportion of subjects with all-cause graft failure (ie, return to permanent dialysis and/or removal of the transplanted kidney and/or clinical determination of cessation of graft function) at 4 years following treatment of the initial qualifying AMR episode. The FAS population will be used to report the efficacy data for all-cause graft failure. Subjects who do not have the key secondary efficacy endpoint assessed post-dose will be assigned as failures.

The proportion of subjects with all-cause graft failure will be summarized by treatment group. Subjects with an assessment of all-cause graft failure or who drop out due to graft failure will be included in the hypothesis testing.

The test statistics and boundary values for decision making at the 3 analyses (2 interim and 1 final) will be specified in the SAP.

The null hypothesis for the proportion of subjects with all-cause graft failure post-treatment will be tested at the overall accumulative alpha level of 0.025 (1-sided test). This hypothesis will only be tested if testing for the primary endpoint of new or worsening TG at 6 months of initiation of treatment is statistically significant.

A number of sensitivity analyses will be performed to assess any impact on the key secondary endpoint results, inference, and conclusions due to missing data. In addition, descriptive analyses on the key secondary endpoint will be provided in selected subgroups.

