In addition to the qualifying kidney biopsy, an additional kidney biopsy will be obtained at the Month 6 study visit. Biopsy slides and pertinent micrographs for the qualifying and Month 6 biopsies will be provided to an independent, blinded pathology EAC for the assessment of the primary endpoint (new or worsening TG at 6 months of initiation of treatment) and other histological changes from baseline. Electron microscopy images will also be used for exploratory analyses of GBM double contouring and endothelial swelling and the effect on long-term graft survival where these changes are observed only on EM. Biopsy slides and pertinent micrographs indicating a new AMR episode or the resolution of an AMR episode will also be provided to the pathology EAC.

Subjects will remain in the study until the clinical confirmatory endpoint of all-cause graft failure is evaluated up to a maximum of 4 years. Graft failure is evaluated by the nephrology EAC. Graft failure, for the purpose of this study, will be defined as 1 or more of the following: (1) institution of permanent dialysis (defined as dialysis treatment >30 days), (2) current transplant nephrectomy, or (3) clinical determination of cessation of kidney graft function and eGFR  $\leq 15$  mL/min/1.73m^2. If a subject is discontinued for any reason prior to the Month 6 follow-up visit, every effort will be made to obtain AEs, serum blood urea nitrogen (BUN) and creatinine (Cr) results, eGFRMDRD, and a biopsy to send slides and images to the pathology and nephrology EACs for determination of TG and graft function status, respectively (see [Table 2](#) for Early Discontinuation Visit procedures). If a subject is discontinued for any reason prior to the end of the study at 4 years, every effort will be made to obtain AEs, serum BUN and Cr and eGFRMDRD results to send to the nephrology EAC for determination of graft function status.

There will be 2 analyses (1st and 2nd interim analyses) assessing the primary endpoint of new or worsening TG at 6 months after initiation of treatment. In addition, there will be 3 analyses (3rd and 4th interim analyses plus 1 final analysis) of proportions of subjects with all-cause graft failure, at approximately 50% (~26 events), 75% (~39 events) and 100% (~51 events) of the

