## 10.2 Key Secondary Efficacy Endpoint(s) and Analysis

The key secondary endpoint is defined as the proportion of subjects with all-cause graft failure at 4 years following treatment of the initial qualifying AMR episode. The graft failure is defined as 1 or more of the following: (1) institution of permanent dialysis, (2) current transplant nephrectomy, or (3) clinical determination of cessation of kidney graft function in any subject that had received a pre-emptive kidney transplant prior to starting dialysis. The FAS will be used for analyzing the key secondary endpoint. Subjects who discontinued prior to 4 years (i.e. Month 48) will be considered 'missing assessment for graft failure at 4 years' and assigned as failures.

The hypothesis of the key secondary endpoint will only be tested if the testing for the primary endpoint of new or worsening TG at 6 months is statistically significant.

The key secondary analysis specified below will be performed based on the FAS. As a sensitivity analysis, the key secondary analysis will be also performed based on Per-protocol Analysis Set-2.

The key secondary endpoint will be presented as the proportion of subjects with all-cause graft failure, and their difference between treatments ( $\Delta_{Cinryze-Placebo}$ ) is defined as follows:

$$\Delta_{Cinryze-Placebo} = \Pi_{Cinryze} - \Pi_{Placebo}$$

Where  $\Pi_{Cinryze}$  is the proportion of all-cause graft failure post-treatment in the CINRYZE group and  $\Pi_{Placebo}$  is the proportion of all-cause graft failure post-treatment in the placebo group.

The analysis will employ a type I error rate of 0.025 to test null hypothesis:

$$H_0 : \Pi_{Cinryze} - \Pi_{Placebo} \geq 0$$

Against the 1-sided alternative:

$$H_a : \Pi_{Cinryze} - \Pi_{Placebo} < 0$$

The key secondary endpoint will have 3 analyses (2 interim and 1 final), at approximately 50% (~26 events), 75% (~39 events) and 100% (~51 events) of the targeted all-cause graft failure. The purpose of the interim analyses is to consider early stopping of the study for claiming of efficacy.

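### SAP 10.2 limits the loss-of-function criterion for graft failure to pre-emptive transplant recipients, a limit found in no other definition, so the key secondary test can omit failures that count toward the event target

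*SAP*

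**What the plan says.** SAP 2.1 states the study-wide definition: "Graft failure is evaluated by the nephrology EAC. Graft failure, for the purpose of this study, will be defined as 1 or more of the" three listed events. These are dialysis for more than 30 days, nephrectomy of the current transplant, and "clinical determination of cessation of kidney graft function and eGFR" of 15 mL/min/1.73m² or less. Nothing restricts who can meet the third. Protocol 3.1 and the synopsis methodology agree: "institution of permanent dialysis (defined as dialysis treatment >30 days), (2) current transplant nephrectomy, or (3) clinical determination of cessation of kidney graft function", with the same eGFR limit. Protocol 7.2.2.5 also applies cessation with eGFR of 15 or less to any subject. It mentions pre-emptive recipients only when describing which dialysis date to record.

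SAP 10.2 then defines the key secondary endpoint again: "The graft failure is defined as 1 or more of the following: (1) institution of permanent dialysis, (2) current transplant nephrectomy", and as the third criterion "clinical determination of cessation of kidney graft function in any subject that had received a pre-emptive kidney transplant prior to starting dialysis". It gives no eGFR limit.

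Protocol 9.8.2.1 and the synopsis endpoint have a third form: "return to permanent dialysis and/or removal of the transplanted kidney and/or clinical determination of cessation of graft function". This has neither the eGFR limit nor the pre-emptive limit. SAP 10.3 dates graft failure by dialysis, nephrectomy or clinical determination, with no pre-emptive limit.

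The study runs to 51 events adjudicated by the nephrology EAC, with looks at about 26, 39 and 51. SAP 10.2 scores subjects who discontinue before Month 48 as failures. SAP 17 does not mention the pre-emptive clause among the changes from the protocol. It does say that the key secondary analysis will not be conducted, because the study was stopped for futility after the first interim analysis.

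**The concern.** The event count that times the looks and the variable that enters the test should rest on one definition. As written they need not. The EAC's role is stated alongside the SAP 2.1 and Protocol 3.1 definition, and the 51-event target is expressed in adjudicated events. The Fisher test is specified in the section carrying the narrower criterion.

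Study success requires significance on this endpoint after the primary, and SAP 10.2 treats the result as confirming clinical benefit. The proportion at 4 years (SAP 10.2) and the time-to-event analysis of the same outcome (SAP 10.3) could also classify the same subject differently.

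**Working it through.** **1. The definitions side by side**

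| Section | Who can meet criterion 3 | eGFR limit |
|---|---|---|
| SAP 2.1, Protocol 3.1, synopsis methodology | any subject | 15 or less |
| Protocol 7.2.2.5 | any subject | 15 or less |
| Protocol 9.8.2.1, synopsis endpoint | any subject | none |
| SAP 10.3 (dating rule) | any subject | none |
| SAP 10.2 | pre-emptive recipients only | none |

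The pre-emptive limit appears once. The missing eGFR limit is shared by SAP 10.2 and the protocol's own endpoint section.

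**2. Which subjects are classified differently**

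- *Counted toward the looks, not in the test:* a recipient dialysed before transplant, with cessation of function and eGFR of 15 or less, no permanent dialysis, no nephrectomy, and still followed at Month 48.
- *In the test, not toward the looks:* a pre-emptive recipient with a clinical determination of cessation but eGFR above 15.

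**3. The plan's own figures reproduce**

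Inputs from SAP 2.5: AMR failure 64% and 25%, other-cause failure 12% in both arms, 100 subjects, one-sided 0.025.

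- All-cause rate = 1 − (1 − AMR)(1 − other). Placebo: 1 − 0.36 × 0.88 = 0.683. CINRYZE: 1 − 0.75 × 0.88 = 0.340. Stated: 68% and 34%.
- The two-proportion formula at 90% power gives 44 per arm without continuity correction and 50 with it, hence 100. Then 100/0.9 = 111.1, rounded up to 112.
- Events: 50 × 0.68 + 50 × 0.34 = 34 + 17 = 51.
- The Hwang-Shih-DeCani boundaries (phi = −4) come out at 0.0030, 0.0075 and 0.0221, as stated.
- Exact Fisher power at 50 per arm, summing binomial probabilities over all tables with one-sided p at or below the level, is 91.5% at 0.025 and 89.4% at 0.0221.

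**4. Illustration of the pre-emptive clause**

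Assume a share f of failures, equal in both arms, goes uncounted. The documents give no value for f. Rates become 0.68(1 − f) and 0.34(1 − f), and events become 51(1 − f).

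| f | Rates | Events | Fisher power at 0.0221 |
|---|---|---|---|
| 0 | 68.0% / 34.0% | 51 | 89.4% |
| 5% | 64.6% / 32.3% | 48.5 | 85.7% |
| 10% | 61.2% / 30.6% | 45.9 | 82.1% |
| 20% | 54.4% / 27.2% | 40.8 | 73.8% |

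**5. Illustration of the missing eGFR limit**

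Assume a share g of non-failures, equal in both arms, is added. Rates become 0.68 + 0.32g and 0.34 + 0.66g.

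| g | Rates | Events | Fisher power at 0.0221 |
|---|---|---|---|
| 5% | 69.6% / 37.3% | 53.5 | 86.2% |
| 10% | 71.2% / 40.6% | 55.9 | 82.9% |
| 20% | 74.4% / 47.2% | 60.8 | 74.4% |

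The two departures move the event count in opposite directions. Under SAP 10.2 itself, additions can come only from pre-emptive recipients. Under Protocol 9.8.2.1 they could come from anyone. All power figures are for a single test at the final level and ignore the interim looks.

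**The case against.** The strongest objection is that nothing to be reported depends on this clause. SAP 17 cancels the key secondary analysis, and SAP 20 marks its tables as not produced. Graft failure appears only in listings, including the nephrology EAC assessment. This stands, and it lowers the urgency. It does not make the stated definition right.

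Second, few subjects may be affected. Anyone who later starts permanent dialysis is counted under the first criterion, and anyone who discontinues before Month 48 is assigned as a failure. This stands for the main analysis and makes the affected group narrow. It is not complete: a subject still followed at Month 48 is not recovered. Sensitivity analyses 1 and 3 replace assigned failure with multiple imputation for those who left.

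Third, adjudication may govern in practice. SAP 2.1 gives the evaluation to the nephrology EAC, whose charter is not among the documents. However, SAP 10.2 does not say that the EAC's finding overrides its own definition, so the text leaves this open.

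A reader might also infer that SAP 10.2 abandons the 30-day dialysis condition. The documents do not support that, because SAP 2.1 defines permanent dialysis as more than 30 days for the whole study and SAP 10.2 uses the same term. Nor does the missing eGFR limit originate in SAP 10.2, since Protocol 9.8.2.1 and the synopsis endpoint also lack it.

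**Conclusion.** SAP 10.2 is wrong as written on one element: the pre-emptive clause conflicts with every other graft-failure definition and is not declared as a change. Followed literally, the key secondary test would omit some failures that count toward the looks. The missing eGFR limit is a separate inconsistency, shared with the protocol's endpoint section, that can add events.

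A reader might infer a definite loss of power, or that every failure without dialysis or nephrectomy in a previously dialysed recipient would be scored as graft survival. The documents support neither. They do not give the share of pre-emptive recipients or of failures meeting only the third criterion, later dialysis or discontinuation recovers many cases, and the eGFR omission acts in the opposite direction. The fall from 89.4% to 82.1% or 73.8% is an illustration at assumed shares of 10% and 20%, not an estimate. The net effect cannot be fixed from the documents.

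That adjudication follows the wider definition rests on SAP 2.1 and Protocol 3.1, without sight of the charter. The point is worth correcting, but it is not critical to the abbreviated report, because the test will not be run.

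**What to change.** - In SAP 10.2, delete the pre-emptive clause and define the endpoint as graft failure adjudicated by the nephrology EAC under the SAP 2.1 and Protocol 3.1 definition, by cross-reference so that the text exists once.
- Align Protocol 9.8.2.1 and the synopsis endpoint with that definition, including the eGFR limit.
- Reconcile footnote a to Table 2 in both documents, which describes the 51 events as including death, while none of the graft-failure definitions lists death as a criterion.

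The SAP change is wording only. The protocol sections need a matching wording amendment. No new data, visits or sample size are involved, and no planned table in the abbreviated report changes.

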4.5 Discontinuation or Withdrawal of Subjects

A subject may withdraw from the study at any time for any reason without prejudice to their future medical care by the physician or at the institution. The investigator or sponsor may withdraw the subject at any time (eg, in the interest of subject safety). The investigator is encouraged to discuss withdrawal of a subject from the study with the medical monitor when possible.

If a subject is discontinued from the study (not only from treatment) for any reason prior to the Month 6 follow-up Visit, every effort will be made to obtain AEs, serum BUN and Cr results, eGFR_{MDRD}, and a biopsy to send to the pathology and nephrology EACs for determination of TG and graft function status, respectively (see Table 2 for Early Discontinuation Visit procedures). If a subject is discontinued from treatment for any reason for the remainder of a treatment cycle for before receiving 7 doses, the subject will continue in the study and no Early Discontinuation Visit will be performed. In this instance, the next scheduled treatment visit in the treatment cycle should be conducted and all procedures for that visit should be performed other than those related to study drug administration, and the scheduled Day 25 post-treatment visit will follow (any remaining treatment visits for that cycle are not required). If a subject is discontinued from the study for any reason after the Month 6 visit and prior to the end of the study at 4 years, every effort will be made to obtain AEs, serum BUN and Cr and eGFR_{MDRD} results to send to the nephrology EAC for determination of graft function status (see Table 2 for End of Study Visit procedures).

Whenever possible and with the consent of the subject, the investigator will attempt to obtain information on graft and subject survival status from discontinued subjects at remaining scheduled assessment times through Month 48. The reason for termination, date of stopping investigational product, and the total amount of investigational product taken must be recorded in the case report form (CRF) and source documents.

Subjects who discontinue will not be replaced. Approximately 112 eligible subjects with biopsy-proven AMR will be randomized to provide 56 subjects per treatment arm. Additional eligible subjects may be enrolled based on the interim data analysis of the first 30 subjects who complete the Month 6 TG assessment (Section 9.5.1).

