6.2.4 Unblinding the Treatment Assignment

The treatment assignment must not be broken during the study except in the following situations:

1. Emergency situations where the identification of the investigational product is required for further treatment of the subject. The investigator should contact the Sponsor's representative(s) not affiliated with the core team as soon as possible after the subject has been unblinded.
2. The first interim analyses for sample size re-estimation after the first 30 subjects complete the Month 6 TG assessment. Only the DMC members will be unblinded for this interim analysis.
3. The second interim analysis is conducted when an adequate number of subjects complete the Month 6 TG assessment for the primary endpoint. The adequate number of subjects will be determined based on the first interim analysis. When the criterion to conduct the second interim analysis is met, treatment assignment for those subjects will be unblinded to designated sponsor representatives for analysis. The treatment assignments for all other subjects will be blinded to the EACs, investigator, and subjects during the conduct of the study.
4. When approximately 50% (~26 events), 75% (~39 events), and 100% (~51 events) of the study information (ie, total number of subjects with all-cause graft failure) is collected. Only the DMC members will be unblinded for the 50% and 75% time points in these interim analyses.

In the event that the treatment assignment is broken, the date, the signature of the person who broke the code, and the reason for breaking the code are recorded on the source documents. Upon breaking the blind, the subject is withdrawn from the study, but should be followed up for safety purposes. Any code-breaks that occur must be reported to the contract research organization (CRO) and the Sponsor's representative(s). Code-break information is held by the pharmacist/designated person at the site and by the CRO Medical Monitor for the study or designee.

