The difference between treatments will be evaluated by a Fisher's Exact test. If the p-value from the test is  $\leq 0.0030$  at first interim analysis (~50% of events), or  $\leq 0.0075$  at the second interim analysis (~75% of events), or  $\leq 0.0221$  at the final analysis (~100% of events), it will be concluded that CINRYZE is efficacious based on the proportion of subjects with all-cause graft failure and the result will serve as confirmatory evidence of clinical benefit based on all enrolled subjects.

Sensitivity analyses will be done at final analysis by using multiple imputation (MI) assuming missing at random (MAR) to assign missing key secondary endpoint and/or by using Cochran–Mantel–Haenszel (CMH) test for treatment effect. The CMH model will assess the treatment effect with controlling for (1) donor characteristic (living vs deceased), (2) baseline AMR severity (severe vs mild to moderate), and possibility (3) time to onset of qualifying AMR from current transplant ( $>100$  days vs  $\leq 100$  days) if degree of freedom allows. All the sensitivity analyses defined below will be based on the FAS.

	Statistical Test	Logic to assign the missing assessments for graft failure at 4 years (i.e. discontinued prior to 4 years)
Key Secondary Analysis Model	Fisher's Exact	Assign failure for subjects who discontinued prior to 4 years.
Sensitivity analysis 1	Fisher's Exact	MI for subjects who discontinued prior to 4 years.
Sensitivity analysis 2	CMH	Assign failure for subjects who discontinued prior to 4 years.
Sensitivity analysis 3	CMH	MI for subjects who discontinued prior to 4 years.

For multiple imputation for the key secondary endpoint, a monotone missing pattern will be assumed. The prediction model will consider treatment group, , AMR severity baseline, donor characteristic as factors with available post-dose eGFR results incorporated. The imputation seed will be 83789524 and number of imputations will be set as 100.

For sensitivity analysis 1, multiple imputation will be used to impute the key secondary endpoint outcome for all subjects who discontinued prior to 4 years. The p-values from Fisher's Exact tests will be computed for each imputed dataset and transformed to  $\chi^2$ -distribution with  $df = 2$  using Fisher's transformation as:

$$\Psi^{(m)} = -2 \log(p^{(m)}) \sim \chi_2^2$$

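### SAP 10.2 codes every subject who discontinued before Month 48 as a graft failure, even if Month 48 graft status was obtained; this is wider than Protocol 9.8.2.1 and does not match how dropouts enter the sample size

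*SAP*

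**What the plan says.** SAP 10.2 defines the missing-data rule by study exit. "Subjects who discontinued prior to 4 years (i.e. Month 48) will be considered" as missing the 4-year assessment, and they are coded as failures. The table in the same section gives the primary-model rule as "Assign failure for subjects who discontinued prior to 4 years". The test is Fisher's exact test on the FAS, with one-sided levels 0.0030, 0.0075 and 0.0221 at about 26, 39 and 51 events.

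Protocol 9.8.2.1 defines the rule by assessment: "Subjects who do not have the key secondary efficacy endpoint assessed post-dose will be assigned as failures". It names no time point. It adds: "Subjects with an assessment of all-cause graft failure or who drop out due to graft failure will be included in the hypothesis testing".

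Protocol 4.5 has investigators try to collect "graft and subject survival status from discontinued subjects at remaining scheduled assessment times through Month 48". This is qualified by "Whenever possible and with the consent of the subject". Exit from the study also need not reflect the graft. Protocol 6.2.4 says of a code break: "Upon breaking the blind, the subject is withdrawn from the study".

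SAP 2.5 states 90% power for 100 subjects at 68% v 34%, one-sided 0.025, and raises 100 to 112 for 10% dropout. SAP 17 lists changes from the protocol. It says the key secondary analysis will not be conducted, and it does not mention the wider failure rule.

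**The concern.** A subject can leave the study, have a functioning graft documented at Month 48 under Protocol 4.5, and still be counted as a failure under SAP 10.2. Under the protocol's wording that subject has been assessed. For discontinued subjects with no later status, reading them as not assessed at 4 years is fair, and the two documents then agree.

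The sensitivity analyses in the table do not help. In analysis 1, "multiple imputation will be used to impute the key secondary endpoint outcome for all subjects who discontinued prior to 4 years". Analysis 3 imputes the same subjects, and analysis 2 repeats the failure rule. None of them uses known status.

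This was the planned confirmatory clinical endpoint. Coding functioning grafts as failures narrows the difference, because at the design rates more of the miscoded subjects are in the CINRYZE arm. It also makes the test depend on who leaves the study. And the sample size removes dropouts from the denominator, while the analysis puts them in the numerator.

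**Working it through.** **Inputs.** From SAP 2.5: failure 68% placebo and 34% CINRYZE, 100 subjects for 90% power at one-sided 0.025, 10% dropout, 112 randomised (56 per arm). From SAP 2.6 and 10.2: Fisher's exact test, final level 0.0221. Assumed: dropout unrelated to outcome and equal by arm unless stated. Power is exact, enumerating all pairs of binomial outcomes with the one-sided Fisher p-value. Each figure is for a single look at the level shown, with 4-year outcomes complete.

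**The plan's own figure.** The composite rates reproduce: 1 − (1 − 0.64)(1 − 0.12) = 68.3% and 1 − (1 − 0.25)(1 − 0.12) = 34.0%. So do the events: 50 × 0.68 + 50 × 0.34 = 34 + 17 = 51. A continuity-corrected two-proportion formula gives 50 per arm, which matches the stated 100. Exact Fisher power at 50 v 50 is 91.5% at 0.025 and 89.4% at 0.0221. Inflation is 100 / 0.90, rounded up to 112. The 90% is therefore not an arithmetic error.

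**Power under the coding rule.** If a share r of dropouts has Month 48 status obtained and used, the coded failure rate is

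p + (1 − p) × dropout × (1 − r).

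Under SAP 10.2, r = 0 whatever was collected:
- placebo: 0.68 + 0.32 × 0.10 = 71.2%
- CINRYZE: 0.34 + 0.66 × 0.10 = 40.6%
- difference: 30.6 points instead of 34

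Power with 56 per arm and 10% dropout:

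| Share of dropouts with status used | Coded rates, placebo v CINRYZE | Power at 0.0221 |
|---|---|---|
| None (SAP rule, or protocol rule with nothing recovered) | 71.2% v 40.6% | 87.0% |
| Half | 69.6% v 37.3% | 90.5% |
| All | 68.0% v 34.0% | 93.4% |

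At 0.025 the first row is 87.3%.

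The number of subjects who could be miscoded is small. Dropouts with a functioning graft at Month 48 number 56 × 0.10 × 0.66 = 3.7 on CINRYZE and 56 × 0.10 × 0.32 = 1.8 on placebo, about 5.5 of 112.

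**False positives.** Both arms at 51% failure, 56 per arm, nominal 2.21%, SAP rule:
- equal 10% dropout: 1.4%
- 5% CINRYZE v 15% placebo: coded 53.5% v 58.4%, giving 4.7%
- mirror case, 15% CINRYZE v 5% placebo: 0.3%

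**The opposite danger.** Suppose dropouts leave just before graft failure and are coded by their functioning graft at exit. With 15% CINRYZE v 5% placebo dropout, the coded rates are 0.51 − 0.15 = 36% v 0.51 − 0.05 = 46%, and false positives reach 12.9%. Assigning failure to unknown status keeps 1.5% in that case.

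**The case against.** Several counter-arguments have force.

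- Protocol 9.4 leaves missing-data handling to the SAP, and Protocol 9.8.2.1 gives no time point, so the SAP had to define missing. This stands for subjects with no later status. It does not explain overriding a status that was obtained.
- SAP 10.2 also plans an analysis on Per-protocol Set-2, and SAP 10.3 plans time to graft failure, which censors discontinued subjects without failure at their last graft assessment. The second does avoid coding them as failures, but it is a secondary analysis and not the confirmatory test. The first changes the population and states no different coding.
- The shortfall is small and depends on the method. An uncorrected normal approximation at the coded rates gives 91.4% at 0.025 and 90.5% at 0.0221. The SAP specifies Fisher's test, however. If every dropout would otherwise have kept the graft (78% v 44%), power would be about 94%.
- Failure imputation is a defensible convention that protects against informative dropout, as the 12.9% v 1.5% comparison shows. This stands, and the fix keeps it for unknown status.

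A reader might infer that the SAP's wider rule alone takes the trial below 90%. It does not: with nothing recovered, the protocol rule read at 4 years gives the same 87.0%. A reader might also infer that the rule inflates type I error. With equal dropout it does not, with unequal dropout the error moves either way, and the documents support neither unequal pattern.

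**Conclusion.** The conflict is real for discontinued subjects whose Month 48 graft status was obtained: failures under SAP 10.2, assessed subjects under Protocol 9.8.2.1. None of sensitivity analyses 1 to 3 uses their status.

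On size, power under the SAP coding is about 3 points below the stated 90% at the planned dropout. That gap comes from sizing the trial as if dropouts were lost and then analysing them as failures. The part due to the SAP's wider rule is the cost of ignoring status in hand: up to about 6 points (93.4% to 87.0%) if all of it was obtained, about 3.5 (90.5% to 87.0%) if half was. These figures rest on the design rates, Fisher's test, and dropout that is equal by arm and unrelated to outcome. The documents do not say how much post-exit status could be recovered.

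SAP 17 cancels the analysis after the futility stop. The point therefore concerns the plan as written and the record of changes, and it should not be read as casting doubt on a reported result.

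**What to change.** Keep Fisher's test, the three looks and the boundaries, and change the coding in SAP 10.2:

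- Code a discontinued subject by graft status at Month 48 (or at the data cut if the study ends at event 51) when it was obtained and confirmed by the nephrology EAC. Assign failure only when it is unknown. Do not carry a functioning graft at exit forward as the 4-year status.
- In analyses 1 and 3, impute only unknown status.
- Keep all-discontinued-as-failure as a sensitivity analysis.
- Restate the power for the coding actually used: about 87% at the final look with 10% dropout and no recovered status. Label any three-look figure as dependent on assumed accrual and hazards, which the documents do not give.

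The change needs no extra patients, but it is not free. The stated power falls below 90%. Later status needs consent, site effort and a route to the EAC, which the documents describe only for data taken at discontinuation. Unequal recovery can bring back part of the bias: with 10% dropout per arm and status obtained for 75% of CINRYZE v 25% of placebo dropouts, false positives are 2.7% against nominal 2.21%.

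Because the analysis is cancelled, the minimum is to reconcile Protocol 9.8.2.1 with SAP 10.2 and record the difference in SAP 17.
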